5.3. Patient Information and Consent

The Investigator will explain the benefits and risks of participation in the study to each patient, the impartial witness and obtain written informed consent. Written informed consent must be obtained prior to the patient entering the study and before initiation of any study related procedure (including administration of investigational drug).

The Sponsor or their designee will provide a sample informed consent form, based on the elements of informed consent in Section 18.1. The final version-dated form must be agreed to by the IRB/IEC and will contain all elements in the sample form, in language readily understood by the patient. In the event the patient is unable to read or write, an impartial witness should be present during the entire informed consent discussion. After the patient has orally consented to participation in the trial, the witness' signature on the form will attest that the information in the consent form was accurately explained and understood. Each patient's original consent form, personally signed and dated by the patient or witness, and by the person who conducted the

informed consent discussion, will be retained by the Investigator. The Investigator will supply all enrolled patients with a copy of their signed informed consent.

The consent form may need to be revised during the study due to a protocol amendment or should important new information become available that may be relevant to the safety of the patient. In this instance approval should always be given by the IRB/IEC and existing patients informed of the changes and re-consented, as directed by the IRB/IEC and in accordance with its policies and procedures. However, in some instances where an immediate change is necessary to eliminate an apparent hazard to patients, then it would not be necessary for a protocol amendment to receive IRB/IEC review and approval before being implemented (21CFR 56.108(a)(4)). Those patients who are presently enrolled and actively participating in the study should be informed of the change if it might relate to the patients' willingness to continue their participation in the study (21CFR 50.25(b)(5)). The FDA does not require re-consenting of patients that have completed their active participation in the study, or of patients who are still actively participating when the change will not affect their participation, for example when the change will be implemented only for subsequently enrolled patients.

The Investigator should, with the consent of the patient, inform the patient's primary physician about participation in the clinical study.

8. STUDY OBJECTIVES AND ENDPOINTS

8.1. Study Objectives

8.1.1. Primary Study Objective

The primary objective of the study is to compare the efficacy of RPC1063 vs placebo for induction of clinical remission at Week 8 in patients with moderately to severely active UC.

8.1.2. Secondary Study Objectives

The secondary objectives are to:

- Compare the efficacy of RPC1063 vs placebo at weeks 8 and 32 as measured by clinical response, clinical remission, and mucosal healing
- Compare the overall safety and tolerability of RPC1063 vs placebo for the duration of the study

[REDACTED]

8.2. Endpoints

8.2.1. Efficacy Endpoints

Primary Efficacy Endpoint:

- The primary endpoint is the proportion of patients in clinical remission at Week 8, defined as a Mayo score of ≤ 2 points and with no individual subscore of > 1 point

Secondary Efficacy Endpoints:

- Proportion of patients with a clinical response at Week 8, defined as a reduction from baseline in Mayo score of ≥ 3 points and $\geq 30\%$, and a decrease from baseline in the rectal bleeding subscore of ≥ 1 point or an absolute rectal bleeding subscore of ≤ 1 point
- Change from baseline in Mayo score at Week 8
- Proportion of patients with mucosal healing at Week 8, defined by an endoscopy subscore of ≤ 1 point

- Proportion of patients in clinical remission at Week 32 defined as Mayo score of ≤ 2 points with no individual subscore of > 1 point
- Proportion of patients with a clinical response at Week 32, defined as a reduction from baseline in Mayo score of ≥ 3 points and $\geq 30\%$, and a decrease from baseline in the rectal bleeding subscore of ≥ 1 point or an absolute rectal bleeding subscore of ≤ 1 point
- Proportion of patients with mucosal healing at Week 32, defined by an endoscopy subscore of ≤ 1 point

[REDACTED]

[REDACTED]

- [REDACTED] at Week 8 as determined by a Geboes index score < 2.0 ([Geboes 2000](#))

8.2.2. Safety Endpoints

- The incidence and type of AEs, SAEs, AEs leading to discontinuation of investigational drug, target AEs of special interest, laboratory abnormalities, vital signs, ECG, and physical exam abnormalities

8.2.3. PK and PD Endpoints

- PK assessments will include PK sampling to determine plasma concentration of RPC1063 and active metabolites at scheduled assessments during the treatment period (see [Table 1](#) [IP and MP] and [Table 2](#) [OLP] Schedule of Events)
- Absolute lymphocyte count (ALC) derived from blinded hematology laboratory results
- Plasma protein biomarkers (cytokines, chemokines, other inflammatory proteins)
- Stool analysis for fecal biomarkers – fecal lactoferrin and calprotectin
- Total immunoglobulins (Igs) - IgA, IgG, IgM

9. INVESTIGATIONAL PLAN

9.1. Overall Study Design and Plan

Study RPC01-202 is a Phase 2, multi-center, randomized, double-blind, placebo-controlled, parallel-group study in patients with moderately to severely active UC.

This study includes 3 periods (Screening, Induction, and Maintenance) and an optional Open-Label Treatment Period (OLP). Following the 5-week Screening Period, eligible patients will be randomized and enter the 9 week placebo-controlled IP. Patients who are responders at Week 8 will continue on their assigned treatment in the 24-week MP. Non-responders at Week 8 have the option to enter the OLP. Patients who complete the MP will be given the option to participate in the OLP. Patients that enter the MP and experience disease relapse will also have the option to enter the OLP.

The study will include both anti-TNF patients as well as anti-TNF naïve patients. It is anticipated that approximately 50% of the patients enrolled will have had prior anti-TNF therapy experience.

The study design is shown in [Figure 1](#). Assessments and procedures are outlined in [Table 1](#) for the IP and MP and [Table 2](#) for the OLP. Assessments are described in [Section 11](#).

Induction Period (IP)

The IP will serve as a dose-finding study to assess the efficacy and safety of RPC1063 for the induction of clinical response, remission, and mucosal healing in patients with moderately to severely active UC. The IP will last 9 weeks and consists of dose escalation over 8 days followed by the full dose for 8 weeks.

Approximately 180 patients will be randomized in a 1:1:1 ratio to receive 1 of 3 treatment regimens:

- RPC1063/ozanimod HCl 0.5 mg (equivalent to ozanimod 0.46 mg) daily oral capsule
- RPC1063/ozanimod HCl 1 mg (equivalent to ozanimod 0.92 mg) daily oral capsule
- Placebo daily oral capsule

The randomization will be stratified by prior anti-TNF therapy experience (yes or no).

For patients randomized to one of the active treatment groups, there will be an 8-day dose escalation regimen in the IP consisting of 4 days of treatment with RPC1063/ozanimod HCl 0.25 mg (equivalent to ozanimod 0.23 mg), followed by 3 days of treatment with RPC1063 0.5 mg, followed by the assigned treatment level for at least 8 weeks.

Maintenance Period (MP)

All patients who complete the IP and are responders (see [Section 13.8](#)) at Week 8 of the IP will enter the 24-week MP. Patients will continue to receive the same investigational drug in the MP as received during the IP, and individual patient treatment will remain blinded until all patients have reached Week 32. The last visit in the MP will occur at Week 32. Patients

who complete the MP will be given the option to participate in the OLP. Patients that enter the MP and experience disease relapse will have the option to enter the OLP.

Optional Open-Label Treatment Period (OLP)

Patients who complete the IP and are non-responders at Week 8 and those that complete the MP or experience disease relapse during the MP will have the option to enter the OLP. All patients in the OLP will receive daily study treatment with RPC1063 1 mg. There will be an 8-day dose escalation regimen consisting of 4 days of treatment with RPC1063 0.25 mg, followed by 3 days of treatment with RPC1063 0.5 mg, followed by RPC1063 1 mg.

Patients who have not shown clinical improvement 8 weeks after initiation of the OLP should discontinue from the study. Eligible patients will be transitioned into the Phase 3 open-label extension UC Study RPC01-3102 and will be able to immediately enter the study (without completing the 30-day or 90-day Safety Follow-up Visits). The OLP will continue for up to 6 years, or until marketing approval of RPC1063 for UC in the country of the clinical site (estimated to be in 2019), or completed transition of patients to Study RPC01-3102, or until the Sponsor discontinues the development program.

Safety Monitoring/Follow-up

Potential AEs of interest that may be a consequence of S1P₁ modulation will be closely monitored during the study. These AEs include bradycardia, heart conduction abnormalities, pulmonary toxicity, macular edema, cutaneous malignancy, serious or opportunistic infection, and hepatotoxicity. A DMC for the study will perform safety reviews periodically, approximately 4 times a year until the end of the Maintenance Period.

The safety of patients will be monitored by collection of treatment-emergent AEs, SAEs, physical exams, vital signs, Holter monitoring and ECGs, PFTs, optical coherence tomography (OCT), blood chemistry and hematology panels, coagulation panels, and urinalysis at baseline and at various time points during the study. White blood cell (WBC) counts and lymphocyte counts will be monitored centrally (and will not be provided to the site) to prevent potential unblinding of the Investigator.

Patients who discontinue from treatment due to lack of response, AEs, or other reasons, even if alternative treatment is given, will be followed for 90 days for collection of safety data and for the assessment of their disease status.

9.1.1. Study Schematic and Schedule of Events

Figure 1: Study Schematic

[figure not shown]

Table 1: Schedule of Assessments and Procedures for Induction and Maintenance Periods

	Study Procedures	Screening	Induction Period (IP)			Maintenance Period (MP)			Safety Follow-up	
			Dose Escalation	Assigned Dose						
			Visit 1 ^{a,b,c}	Visit 4 ^{b,d}	Visit 5 ^{b,d}	Relapse Visit	Visit 6 ^b	End of Study Visit/ET		
			Dose Escalation Day 1	Week 4	Week 8		Week 20	Week 32		
Day -35 to 0	Dose Escalation Day 1	Day 36±3	Day 64±3	Day 1OLP	Day 148±3	Day 232±3	Last dose + 30 days ± 7 days	Last dose + 90 ± 10 days ^r		
	Informed consent	X								
	Inclusion/exclusion criteria	X	X							
	Demographics	X								
	Medical history ^c	X	X							
	TB screening ^f	X								
	Chest X-ray ^f (if not done in previous 6 months)	X								
	Total immunoglobulins (Igs) - IgA, IgG, IgM	X					X			
	Viral serology ^g	X								
	Stool culture ^h	X								
	Randomization		X							
	Dispense investigational drug		X	X	X		X			
	Administer investigational drug at clinic		X							
	Review drug compliance			X	X		X	X		
	Prior and concomitant medications	X	X	X	X		X	X	X	
SAFETY ASSESSMENTS	Adverse events	X	X	X	X		X	X	X	
	12-Lead ECG	X	X ^a		X		X			
	Holter monitoring		X							
	Vital signs	X	X ^a	X	X		X			
	Clinical laboratory tests									
	Hematology ^s	X	X	X	X		X	X		
	Blood chemistry	X	X	X	X		X	X		

Patients not in response or who do not maintain response within this time period should follow the assessments and timings provided in the OLP table (Table 2)

	Study Procedures	Screening	Induction Period (IP)			Maintenance Period (MP)			Safety Follow-up	
			Dose Escalation		Assigned Dose					
			Visit 1 ^{a,b,c}	Visit 4 ^{b,d}	Visit 5 ^{b,d}	Relapse Visit	Visit 6 ^b	End of Study Visit/ET		
			Dose Escalation Day 1	Week 4	Week 8		Week 20	Week 32		
	Day -35 to 0	Dose Escalation Day 1	Day 36±3	Day 64±3	Day 1OLP	Day 148±3	Day 232±3	Last dose + 30 days ± 7 days	Last dose + 90 ± 10 days ^r	
	Pregnancy test (WOCBP only) ⁱ	X	X	X	X		X	X	X	X
	Coagulation panel	X						X		
	Urinalysis	X			X		X	X		
	Physical examination ^j	X	X ^k		X ^k		X ^k	X	X ^k	
	Pulmonary function tests ^l	X ^l			X ^l			X		
	Optical coherence tomography	X						X		
PK AND PD ASSESSMENTS	Stool collection for fecal biomarkers	X			X			X	X	
	Inflammatory biomarkers plasma sampling	X			X			X	X	
	PK blood sampling ^m		X	X	X		X	X	X	X
EFFICACY ASSESSMENTS	Endoscopy ⁿ	X			X ^o			X		
	Mayo scoring									
	Mayo diary	X ^p	X	X	X		X	X		
	Mayo full clinical score	X			X			X		
	Mayo partial clinical score		X ^q	X			X			
	Patient diary to support mayo clinical score	X	X	X	X		X	X		
	Colonic biopsy	X			X			X		

Key: ALC = absolute lymphocyte count; ET = Early Termination; IP = Induction Period; MP = Maintenance Period; OCT = optical coherence tomography; OLP = Open-Label Period; PD = pharmacodynamic; PK = pharmacokinetic; TB = tuberculosis; WOCBP = women of child-bearing potential.

Footnotes to Table 1

- a. The duration of Visit 1 will be approximately 7 hours. Prior to dosing a 12-lead ECG will be performed and following dosing patients will have hourly vital signs recorded at 1, 2, 3, 4, 5 and 6 hours (± 10 minutes) postdose. A further 12-lead ECG will be performed at the end of the observation period.
- b. Study visits should be scheduled in the morning, where possible, and on study visit days patients should be instructed to withhold the dose until the study visit and the dose should be administered during the visit.
- c. Just prior to dosing at Visit 1, patients will begin 24-hours of Holter monitoring. Patients will not be expected to remain on site for the 24-hour duration as monitoring will continue at home.
- d. IP Week 4 and IP Week 8 occur 4 and 8 weeks, respectively, following the completion of dose escalation, ensuring 8 weeks of dosing at the assigned dose.
- e. Medical history will include smoking history. The Day 1 medical history can be abbreviated, noting events that occurred between Screening and Day 1.
- f. Screening for TB will include a review of past history, current physical exam. A chest X-ray will be obtained for those subjects who do not have a chest X-ray within 6 months prior to screening and either a tuberculin skin test or a QuantiFERON[®] gold test for TB.
- g. Serology testing will be performed at screening to determine the patient's immune status with respect to the following viruses: varicella zoster virus (VZV), human immunodeficiency virus (HIV) antibodies, hepatitis B surface antigen (HBsAg) and anti-hepatitis B core antigen (HBcAg) IgM, anti-hepatitis C virus (HCV) IgG or IgM, should be assessed at screening in all patients.
- h. At screening the stool sample should be used to rule out serious infection and should include evaluation for *C. difficile* toxin as well as ova and parasitic examination.
- i. For females of childbearing potential only, serum beta human chorionic gonadotropin (hCG) at screening is required, and a urine beta hCG is required at each visit. Between scheduled visits up until the 90-day Safety Follow-up Visit, monthly home urine pregnancy tests should be performed by the patient. If a urine pregnancy test result is positive, the Investigator will instruct the patient to suspend further RPC1063 dosing, if applicable, and schedule a follow-up appointment as soon as possible. A serum pregnancy test will be performed for confirmation, including after the 90-day Safety Follow-up Visit, if needed.
- j. At screening includes height and weight, and Visits 1, 5, 6, End-of-Study, and 30-day Safety Follow-up Visit includes weight only. A complete PE will be performed at screening and End-of-Study. The complete physical examination will include a full examination of the skin for lesions as well as a check for visual symptoms (i.e., blurred vision or decreased visual acuity).
- k. An interim physical examination will be conducted at Visits 1, 5, 6, and 30-day Safety Follow-up Visit. The interim PE will include areas with previously noted abnormalities and/or that are associated with any new complaints from the patient. The interim PE will also include a check for visual symptoms (i.e., blurred vision or decreased visual acuity).
- l. DLCO, if applicable, will be done at Screening and End of Study/ET.
- m. Blood samples for PK evaluation are to be taken up to 15-30 minutes prior to investigational drug (pre-dose) and just prior to discharge from the clinic (6-8 hours post dose) on Day 1. Blood samples on Week 4 and 20 should be taken 2-6 hours after dosing. Blood samples on Week 8 and 32 will be trough level, taken just prior to dose administration. The actual time of investigational drug administration for all visits with PK evaluation will be recorded on the dosing log. The blood sample at the 30-day and 90-day Safety Follow-up Visits can be collected at any point during the visit. An additional PK sample will be obtained for patients with any AE resulting in unblinding, discontinuation, or SAE.
- n. At screening a colonoscopy will be required if the patient has had UC ≥ 10 years but has not had a colonoscopy within 1 year of the screening date. If the patient has had a colonoscopy within 1 year of the screening date a flexible sigmoidoscopy may be used. Endoscopy must be completed within 21 days of randomization. This procedure can also be used to determine the endoscopy subscore component of the Mayo Score.
- o. At Visit 5, sigmoidoscopy should be performed either on day of visit or no more than 7 days prior to the visit date.
- p. At screening patients will be issued with a Mayo diary and will be trained in the completion of the diary.
- q. The Mayo partial clinical score on Day 1 should be combined with the Central endoscopic read in order to assess the patient for "Mayo Score" entrance criteria.
- r. The 90-day Safety Follow-up Visit should be conducted as a clinic visit. However, if the patient is not available for a clinic visit, a telephone call follow-up should be performed (with at least 3 attempts within the visit window) to record the pregnancy test result, concomitant medications, and AEs, including information regarding relationship of the AE to RPC1063.
- s. If ALC is confirmed < 200 cells/ μL , the Investigator will temporarily discontinue investigational drug and then consult the Medical Monitor. Laboratory testing will be repeated weekly until ALC is > 500 cells/ μL . For patients whose ALC level is confirmed < 200 cells/ μL and has not reached the acceptable range (ALC > 500 cells/ μL) during the study, laboratory testing will be repeated at the 90-day Safety Follow-up Visit.

Table 2: Schedule of Assessments and Procedures for the Optional Open-Label (OLP) Period

	Study Procedures	Open-Label Period (OLP)				End of Open-label Visit/ET ^e	Safety Follow-up ^m	
		Dose Escalation	Assigned Dose (1 mg)					
		Visit 1OLP ^{a,b,c}	Visit 4OLP ^{b,d}	Visit 5OLP ^{b,d}	Additional OLP Visits ^c			
		Dose Escalation Day 1	Week 4OLP	Week 8OLP	12-week Intervals			
	Dose Escalation Day 1OLP	Day 36 ± 3 OLP	Day 64 ± 3 OLP	Day (last visit calculated from Day 1 + 84) ± 14 OLP	Day of last dose	Last dose + 30 ± 7 days	Last dose + 90 ± 10 days ⁿ	
	Dispense investigational drug	X	X	X	X	X ^m		
	Administer investigational drug at clinic	X						
	Review drug compliance		X	X	X	X		
	Prior and concomitant medications	X	X	X	X	X	X	X
SAFETY ASSESSMENTS	Total immunoglobulins (Igs) - IgA, IgG, IgM					X		
	Adverse events	X	X	X	X	X	X	X
	12-Lead ECG	X ^a				X		
	Holter monitoring	X						
	Vital signs	X ^a	X	X	X	X		
	Clinical laboratory tests							
	Hematology ^o		X	X	X	X	X	
	Blood chemistry		X	X	X	X	X	
	Pregnancy test (WOCBP only) ^f		X	X	X	X	X	X
	Coagulation panel					X		
	Urinalysis			X		X		
	Physical examination ^g			X ^h		X ^g	X ^h	
	Pulmonary function tests ⁱ					X		
Optical coherence					X			

	Study Procedures	Open-Label Period (OLP)				End of Open-label Visit/ET ^e	Safety Follow-up ^m	
		Dose Escalation	Assigned Dose (1 mg)					
		Visit 1OLP ^{a,b,c}	Visit 4OLP ^{b,d}	Visit 5OLP ^{b,d}	Additional OLP Visits ^c			
		Dose Escalation Day 1	Week 4OLP	Week 8OLP	12-week Intervals			
	Dose Escalation Day 1OLP	Day 36 ± 3 OLP	Day 64 ± 3 OLP	Day (last visit calculated from Day 1 + 84) ± 14 OLP	Day of last dose	Last dose + 30 ± 7 days	Last dose + 90 ± 10 days ⁿ	
	tomography							
PK AND PD ASSESSMENTS	Stool collection for fecal biomarkers			X		X	X	
	Inflammatory biomarkers plasma sampling			X		X	X	
	PK blood sampling ^j			X		X	X	
EFFICACY ASSESSMENTS	Endoscopy				X ^k	X ^l		
	Mayo scoring							
	Mayo diary		X	X	X	X		
	Mayo full clinical score				X ^k	X		
	Mayo partial clinical score		X	X	X			
	Patient diary to support Mayo clinical score		X	X	X	X		
	Colonic biopsy				X ^k	X		

Key: ALC = absolute lymphocyte count; ET = Early Termination; OCT = optical coherence tomography; OLP = Open-label Period; PD = pharmacodynamic; PK = pharmacokinetic; WOCBP = women of child-bearing potential.

Footnotes to Table 2

- The duration of Visit 1OLP will be approximately 7 hours. Prior to dosing a 12-lead ECG will be performed and following dosing patients will have hourly vital signs recorded at 1, 2, 3, 4, 5 and 6 hours (±10 minutes) postdose. Another 12-lead ECG will be performed at the end of the observation period.
- Study visits should be scheduled in the morning, where possible, and on study visit days patients should be instructed to withhold the dose until the study visit and the dose should be administered during the visit.

- c. Just prior to dosing at Visits 1OLP, patients will begin 24- hours of Holter monitoring. Patients will not be expected to remain on site for the 24-hour duration as monitoring will continue at home.
- d. Visit 4OLP and Visit 5OLP occur 4 and 8 weeks, respectively, following the completion of dose escalation, ensuring 8 weeks of dosing at the assigned dose.
- e. Patients who continue past Week 8 in the OLP will have the Additional OLP Visit assessments performed at 12-week intervals throughout the OLP. The OLP will continue for up to 6 years, or until marketing approval of RPC1063 for UC in the country of the clinical site (estimated to be in 2019), or the completed transition of patients to Study RPC01-3102, or until the Sponsor discontinues the development program.
- f. For females of childbearing potential only, serum beta human chorionic gonadotropin (hCG) at screening is required and a urine beta hCG is required at each visit. Between scheduled visits, monthly urine pregnancy tests should be performed by the patient. If a urine pregnancy test is positive, the Investigator will instruct the patient to suspend further RPC1063 dosing, if applicable, and schedule a follow-up appointment as soon as possible. A serum pregnancy test will be performed for confirmation, including after the 90-day Safety Follow-up Visit, if needed.
- g. Includes weight. The complete physical examination will include a full examination of the skin for lesions as well as a check for visual symptoms (i.e., blurred vision or decreased visual acuity).
- h. An interim physical examination will be conducted at Visit 5OLP and 30-day Safety Follow-up Visit. The interim PE will include areas with previously noted abnormalities and/or that are associated with any new complaints from the patient. The interim PE will also include a check for visual symptoms (i.e., blurred vision or decreased visual acuity).
- i. DLCO, if applicable, will be done at End of Open-Label/ET.
- j. The PK blood sample on Week 8 should be trough level, taken just prior to dose administration. The blood sample on End of Open-label Visit/ET should be taken 2-6 hours after dosing. The actual time of investigational drug administration for all visits with PK evaluation will be recorded on the dosing log. The blood sample at the 30-day and 90-day Safety Follow-up Visits can be collected at any point during the visit. An additional PK sample will be obtained for patients with any AE resulting in unblinding, discontinuation, or SAE.
- k. For patients who continue past Week 8 in the OLP, an endoscopy will be performed at Week 56OLP and a full Mayo score will be calculated at that time.
- l. At End of Open-Label or ET Visit sigmoidoscopy should be performed either on day of visit or no more than 7 days prior to the visit date.
- m. For patients who are entering the open-label extension UC Study RPC01-3102 at a date other than the End of Study visit, investigational drug will be dispensed in this study. For patients who are immediately entering (at the End of Study visit) the open-label extension UC Study RPC01-3102, investigational drug will be dispensed in Study RPC01-3102.
- n. The 90-day Safety Follow-up Visit should be conducted as a clinic visit. However, if the patient is not available for a clinic visit, a telephone call follow-up should be performed (with at least 3 attempts within the visit window) to record the pregnancy test result, concomitant medications, and AEs, including information regarding relationship of the AE to RPC1063.
- o. If the ALC is confirmed below 200 cells/ μ L, the Investigator will temporarily discontinue investigational drug and then consult the Medical Monitor. Laboratory testing will be repeated weekly until ALC is $>$ 500 cells/ μ L. For patients whose ALC level is confirmed $<$ 200 cells/ μ L and has not reached the acceptable range (ALC $>$ 500 cells/ μ L) during the study, laboratory testing will be repeated at the 90-day Safety Follow-up Visit.

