- Routine blood samples will be analyzed by the central laboratory. Blood samples taken at the screening visit are to be in the fasting state. Blood samples taken at subsequent visits are recommended to be in the fasting state. Details regarding collection of samples, shipment of samples, reporting of results, laboratory reference ranges, and alerting abnormal values will be supplied to the site before site initiation in a study laboratory manual. The results of the analysis will be made available to

each site by the central laboratory, at the earliest, 48 hours after receipt of the samples by the central laboratory.

- Investigators will be asked to comment on those abnormalities on the respective laboratory result page, including a notation of the clinical significance of each abnormal finding in the patient's source documents. The laboratory sheets will be filed with the patient's source documents. Abnormal laboratory values should not be recorded on the AE eCRF; however, any diagnoses (or signs or symptoms if a diagnosis is not possible) associated with the abnormal findings should be recorded on the AE eCRF.
- Pregnancy test: serum beta-hCG must be performed at screening in women of childbearing potential. Urine beta-hCG will be performed in women of childbearing potential at each scheduled visit. Between scheduled visits up until the 90-day Safety Follow-up Visit, monthly home urine pregnancy tests should be performed by the patient. If a urine pregnancy test result is positive, the Investigator will instruct the patient to suspend further RPC1063 dosing, if applicable, and schedule a follow-up appointment as soon as possible. A serum pregnancy test will be performed for confirmation, including after the 90-day Safety Follow-up Visit, if needed.
- Coagulation panel: prothrombin time (PT) and partial thromboplastin time (PTT). To be performed as scheduled in [Table 1](#) and [Table 2](#).
- Serology testing will be performed at screening to determine the patient's immune status with respect to several viruses; testing will be as follows:
 - anti-VZV IgG
 - HIV antibodies
 - HBsAg and HBcAg IgM
 - anti-HCV IgG or IgM

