12.9. Procedures in Case of Pregnancy

If a urine pregnancy test is positive, the Investigator will instruct the patient to suspend further RPC1063 dosing. If the test was performed by the patient between scheduled visits, a follow-up appointment will be scheduled as soon as possible. A serum pregnancy test will be performed for confirmation.

Pregnancy in itself is not regarded as an AE unless there is a suspicion that an investigational product may have interfered with the effectiveness of a contraceptive medication. However, the outcome of all pregnancies (spontaneous miscarriage, elective termination, normal birth, or congenital abnormality) must be followed up and documented even if the patient was discontinued from the study.

All reports of congenital abnormalities/birth defects are SAEs. Spontaneous miscarriages should also be reported and handled as SAEs. Elective abortions without complications should not be

handled as AEs. All outcomes of pregnancy must be reported to the Sponsor and/or its designee. In cases of live birth, the infant will be followed for up to a year.

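### Table 2 schedules no pregnancy test at Visit 1OLP, the first active dose for former placebo patients, although its own footnote requires one at every visit

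*Protocol*

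**What the plan says.** Table 2 in Protocol 9.1.1 has seven visit columns: Visit 1OLP, Visit 4OLP, Visit 5OLP, the additional 12-weekly visits, End of Open-label/ET, and the 30-day and 90-day follow-up visits. The row "Pregnancy test (WOCBP only) ^f" is marked in the last six and blank at Visit 1OLP. Visit 1OLP is the only column in which the row "Administer investigational drug at clinic" is marked.

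The written rules make no exception for that visit:

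- Table 2, footnote f: "a urine beta hCG is required at each visit".
- Protocol 11.3: "Urine beta-hCG will be performed in women of childbearing potential at each scheduled visit".
- SAP 6.20.6 also asks for a urine test at each visit and adds that a patient who tests positive is not to be dosed.

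On treatment, Protocol 9.1 says: "All patients in the OLP will receive daily study treatment with RPC1063 1 mg". On a positive result, Protocol 12.9 says: "If a urine pregnancy test is positive, the Investigator will instruct the patient to suspend further RPC1063 dosing".

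Table 1, for the induction and maintenance periods, marks the test at Visit 1, the first-dose visit of the blinded phase. Its Relapse Visit column, headed Day 1OLP, is empty in every row. A note there says that patients who are not in response, or who lose it, "should follow the assessments and timings provided in the OLP table (Table 2").

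**The concern.** The schedule table is what a site works from on the day. Here it and its own footnote disagree, and they disagree at the visit where the test matters most. Everyone entering the open-label period takes RPC1063, so Visit 1OLP is the first exposure to active drug for a patient who was on placebo. Pregnancy is an exclusion at screening (9.5.2) and a listed reason for discontinuation (9.7.1), so the protocol clearly means to avoid exposing a pregnant woman.

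There is a second gap. No visible sentence in the protocol says that the result must be known before the first open-label dose. The instruction after a positive test is to suspend further dosing, which does not in itself prevent that first dose. The bar on dosing after a positive test appears only in the SAP, which sites do not work from.

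The matter is patient safety. Sample size, type I error and the efficacy analyses are unaffected.

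**Working it through.** The plan states no figure to reproduce. The check is a cell count, a comparison of texts and some date arithmetic.

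**1. Is the blank real, or an artefact of the PDF text?** The adverse-event and concomitant-medication rows of Table 2 fill all seven columns, so the column count is sound. The six marks in the pregnancy row could be shifted one column to the left only by removing the 90-day test. Footnote n expects a pregnancy result at the 90-day visit, so that reading fails. The blank is Visit 1OLP.

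**2. Grid against text**

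| Source | Test at first open-label dose? |
|---|---|
| Table 2 grid | No (6 of 7 columns marked; Visit 1OLP blank) |
| Table 2, footnote f | Yes, every visit |
| Protocol 11.3 | Yes, every scheduled visit |
| SAP 6.20.6 | Yes, every visit; no dose if positive |
| Table 1, Visit 1 (matching first-dose visit) | Yes (8 of 9 columns marked; only the Relapse Visit blank) |

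The blank Relapse Visit cell is not separate evidence of an omission, because that whole column is empty. It does mean that a relapsing patient is sent to Table 2, so neither grid shows a test for her when open-label dosing starts.

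**3. Time to the next gridded clinic test.** Visit 4OLP is on Day 36 ± 3 and the first dose on Day 1.

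- 36 − 1 = 35 days
- With the window: 35 − 3 = 32 to 35 + 3 = 38 days
- Taking monthly as about 30 days: 38 / 30 = 1.3, so about one home test in between

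**4. Age of the last scheduled clinic test at the first open-label dose.** Protocol 10.4 allows up to 2 weeks between the qualifying visit and the start of the open-label period.

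- Entry from Week 8, Week 32 or a relapse found at a scheduled visit: at most about 14 days.
- Entry after a relapse between scheduled visits (Protocol 10.6): scheduled tests fall on Days 64, 148 and 232. 148 − 64 = 84 and 232 − 148 = 84 days, if the relapse visit is also Day 1OLP.
- With the ± 3-day windows: (148 + 3) − (64 − 3) = 90 days.
- With the 2-week allowance: 84 + 14 = 98 and 90 + 14 = 104 days.
- Home tests in between: 98 / 30 = 3.3, so about three.

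**5. Ceiling on patients first exposed at Visit 1OLP.** This is the placebo arm: 180 / 3 = 60. The documents give neither the share of women of childbearing potential nor the relapse rate, so the number affected cannot be calculated.

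**The case against.** The best reply is that the test is already required. Footnote f sits on this very row, and a site sent to Table 2 is sent to its footnotes too. On this view one mark is missing from a grid and no safeguard is absent. That is correct as far as it goes, and it limits the risk. It does not remove the conflict between the grid and the footnote.

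A second reply is that the blank may be deliberate. Hematology, chemistry, urinalysis and coagulation are also unmarked at Visit 1OLP, which fits a layout that relies on tests from the qualifying visit. For entry at Week 8 or Week 32 this is reasonable. But those rows carry no rule requiring a test at every visit, and the pregnancy row does. Nor does the layout serve a patient whose relapse is found between visits, since no qualifying test is marked for her on either grid.

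Third, the 84 to 104 day figures are upper limits. They require a relapse just before the next scheduled visit, no test at the relapse visit although Table 1 footnote i also requires one at each visit, and, for the longer values, the full two-week delay. They count clinic tests only. If the monthly home tests are done, the latest result is about a month old. They apply to far fewer women than the ceiling of 60. All of this stands.

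Finally, Section 9.6.7, on dose escalation including Day 1OLP, is largely blacked out in the public copy. An instruction to test before dosing could be there. This limits what can be said about the missing pre-dose condition. It does not affect the conflict between the visible grid and its footnote.

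**Conclusion.** The concern holds. Table 2 omits the pregnancy test at one visit of seven, against three written statements that require it. The omission falls on the first active dose for former placebo patients. The count and the contradiction rest on the visible text alone and are firm. The statement that no pre-dose condition exists applies only to the visible protocol text.

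The practical risk is limited by the written rule, by the contraception required at entry (9.5.1, criterion 6) and by monthly home testing. It is smallest for scheduled entry, where a clinic test is at most about 14 days old. It is greatest for relapses between visits, where the last scheduled clinic test may be about 84 days old, or up to 104 days in the extreme case. How many women are affected is unknown. Because this is an operating schedule governing possible exposure in pregnancy, and the correction is trivial, it should be made.

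**What to change.** Mark the urine pregnancy test at Visit 1OLP in Table 2. Add one sentence to footnote f stating that the result must be negative before the first open-label dose is given. If the redacted part of Section 9.6.7 already says this, a cross-reference to it is enough. The added sentence agrees with SAP 6.20.6.

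The cost is one table cell and one sentence. The text already requires the test, and Visit 1OLP is already a clinic visit of about 7 hours, so there is no new procedure.
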